## Study Design

**Overall strategy.** We will enroll forty adult MS patients (aged 18-65 years) randomly assigned to one of two groups: either a Verum (6 Hz) tACS group or a Frequency Control (1 Hz) group. Twenty participants in each group will correspond with >80% power ( $1-\beta$ ) at a 95% significance level ( $1-\alpha$ ) as calculated from our preliminary studies. The two groups will be age-matched. A randomized double-blinded, placebo controlled, multi-session

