**Secondary outcome measure: Frontal theta power.** Results from Preliminary Study 1 also showed that the Verum tACS group, and not control tACS, exhibited a correlation between divided attention and frontal theta power such that those participants with the greatest increase in frontal theta power yielded the greatest improvement in divided attention ability ( $r = 0.50$ ,  $p = 0.04$ ). Here, it is hypothesized that MS patients who receive Verum tACS will exhibit similar neuroplastic changes in frontal theta activity. To test this, frontal theta power will be extracted during the discrimination task (theta dual task minus theta single task) and a change score will be calculated (post-tACS minus pre-tACS). A regression analysis will be conducted between theta power and the change in the divided attention index (post-tACS minus pre-tACS) described above. It is expected that increases in theta power only the Verum tACS group will be related to improvements in divided attention ability. To further characterize between group differences, theta power will be submitted to an ANCOVA with Group (Verum, Control) and Session (pre-tACS, post-tACS) as factors. Although age will be matched across groups, age will serve as the covariate to account for within-group differences. A Group x Session interaction is expected to show that the Verum tACS group, compared to the control group, will exhibit a larger increase in theta power post-tACS, indicating enhanced neuroplasticity. For this interaction, 20 participants per group will yield  $>95\%$  power ( $1-\beta$ ) at a 95% significance level ( $1-\alpha$ ) with an expected effect size of  $f = 0.28$ .

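### The plan expects theta change to track divided-attention improvement only in the Verum arm, but no planned analysis compares that relation between arms

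*Combined protocol and SAP*

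**What the plan says.** The point sits in the combined protocol and SAP, Statistical Design and Power, under the secondary outcome of frontal theta power.

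- **Model for the hypothesis.** "Results from Preliminary Study 1 also showed that the Verum tACS group, and not control tACS, exhibited a correlation". The variables correlated are theta power and attention, with r = 0.50 and p = 0.04. No control-arm correlation is reported, and no test of the difference.
- **Planned analysis of the relation.** "A regression analysis will be conducted between theta power and the change in the divided attention index", both taken as post minus pre. The text does not say whether this regression is pooled or run by arm, and it names no Group term.
- **Expectation.** "It is expected that increases in theta power only the Verum tACS group will be related to improvements in divided attention ability".
- **Between-arm theta analysis.** "theta power will be submitted to an ANCOVA with Group (Verum, Control) and Session (pre-tACS, post-tACS) as factors", with age as covariate. This is the only analysis in the paragraph with a power figure: above 95% at f = 0.28.

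The Specific Aim 2 regressions (Study Design, Covariates to be included in Regression Analyses) use modelled electric field, evoked potentials, clinical severity, demographics and clinical features. Theta change is not among them.

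**The concern.** A statement that a relation holds in one arm and not in the other is about a difference between two relations. It needs a test or an interval for that difference. A significant result in Verum beside a non-significant one in Control does not supply this, because with 20 per arm two samples from the same population will often fall on opposite sides of the significance threshold. The Group x Session ANCOVA does not fill the gap: it compares mean theta change between arms, not how theta change relates to attention change.

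A relation shared by both arms is plausible on the plan's own account. All participants perform EVO during stimulation, and the Cognitive paradigm section describes frontal theta oscillations as inherent to that task. At stake is whether a theta-attention relation common to both arms could be reported as particular to 6 Hz stimulation.

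**Working it through.** **Inputs from the documents.** 20 per arm ("We will enroll forty adult MS patients (aged 18-65 years) randomly assigned to one of two groups"; the theta paragraph also uses 20 per group). Alpha 0.05 ("at a 95% significance level"). Preliminary Verum correlation 0.50, p = 0.04.

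**Assumptions.** Two-sided testing (sidedness is not stated). Bivariate normal data, coded so that the expected relation is positive. The same true correlation r in both arms, varied because no control-arm value is given.

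**1. The plan's own figures.** The power above 95% belongs to the Group x Session test. With λ = f² × N × 2 / (1 − ρ), f = 0.28, N = 40 and F on 1 and 38 df:
- ρ = 0.5 gives λ = 0.0784 × 80 / 0.5 = 12.5 and power 93.2%;
- power reaches 95% at ρ of about 0.54, and is 97.1% at ρ = 0.6.

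So the figure is reproduced if the unstated pre-post correlation ρ is about 0.54 or more. It says nothing about the regression, for which no power is given.

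For the preliminary result, t = r√(n − 2)/√(1 − r²) with r = 0.50 gives two-sided p = 0.041 at n = 17. The quoted p therefore fits an arm of about 17. That size is inferred, not stated.

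**2. Precision within one arm.** At n = 20 the critical |r| is 0.444. An observed r of 0.50 has a Fisher-z 95% interval of tanh(0.549 ± 1.96/√17), or 0.07 to 0.77.

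**3. Arm-by-arm reading with equal true correlations.** The arms are independent, so

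P(false Verum-only) = P(Verum positive and significant) × [1 − P(Control significant)].

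The component probabilities are by simulation:

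| Common true r | P(Verum positive, significant) | P(Control not significant) | False Verum-only |
|---|---|---|---|
| 0.1 | 0.061 | 0.930 | 6% |
| 0.2 | 0.131 | 0.866 | 11% |
| 0.3 | 0.253 | 0.746 | 19% |
| 0.4 | 0.430 | 0.570 | 24 to 25% |
| 0.5 | 0.642 | 0.358 | 23% |
| 0.6 | 0.835 | 0.165 | 14% |
| 0.7 | 0.957 | 0.043 | 4% |

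At r = 0 the pattern appears in about 2.4%.

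**4. Direct test in the same trials.** A Group x theta-change term (36 residual df) falsely favours Verum in about 2.5% of trials at every r. At the preliminary r of 0.50 the ratio is 23 / 2.5, about 9.

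**5. Pooled reading.** One regression without Group returns one slope. It cannot show a relation in Verum alone, whatever the data.

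**6. Power of the direct test if the relation truly is Verum-only (0.5 versus 0).** Fisher z: difference 0.549, standard error √(2/17) = 0.343, ratio 1.60, power Φ(1.60 − 1.96) = 36%. Simulation gives about 35% for the slope interaction and 37% for the Fisher-z test. For 80% power, n per arm = 2 × [(1.96 + 0.84)/0.549]² + 3 = 55.02, rounded up to 56.

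**The case against.** The strongest reply is that the arm-by-arm rule in step 3 is not in the plan. The text plans a single regression and states an expectation; it sets no decision rule. This stands. A reader might infer that following the plan as written produces the false pattern at the rates shown, but the documents do not go that far. Arm-by-arm judgement is an inference from the hypothesis and from the form of the preliminary result. The gap remains, because the pooled alternative cannot address the expectation either.

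Second, the rates describe the correlation pattern alone. The plan also has randomised Group x Session comparisons of theta and of d-prime cost. If the relation is shared and 6 Hz has no effect on theta, the false pattern together with a theta comparison favouring Verum is rare: about 0.2 to 0.6% of simulated trials for r from 0.2 to 0.5, in line with 2.5% of 11 to 25%. This stands as a limit on the consequence. It does not answer the point, because the plan does not make the Verum-only statement conditional on the ANCOVA.

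Third, a reader might infer that without an interaction nothing can be attributed to 6 Hz. That does not follow. If 6 Hz raises theta in the randomised comparison and theta relates to attention with the same slope in both arms, that is an ordinary mediation pattern, and no interaction is expected. The interaction bears only on the Verum-only wording.

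Nor is that wording the plan's only link between theta and behaviour. The frontal theta outcome description, the Cognitive paradigm section and Preliminary Study 1 each draw one.

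**Conclusion.** The concern holds in a limited form. The plan states a comparative expectation and no analysis that can test it. Read arm by arm, equal relations would give a false Verum-only pattern in about 4 to 25% of trials for a common correlation between 0.1 and 0.7, highest around 0.4 to 0.5, against about 2.5% for a direct test. These rates rest on equal correlations, normality, two-sided testing and 20 evaluable participants per arm; the equal correlation is assumed, not documented. Whether the pattern would be read this way is inferred, so the defect itself is an unspecified and untested comparison. It concerns a secondary outcome and leaves the primary outcomes untouched, but should be corrected before analysis.

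**What to change.** In the frontal theta paragraph of Statistical Design and Power, replace the regression sentence with one model on all participants: change in the divided attention index on theta change, Group and Group x theta change. Report both slopes and their difference, each with a 95% confidence interval. Describe the relation as specific to Verum only if the interaction supports it, and label this analysis exploratory. Otherwise report the theta-attention association without calling it Verum-only. Whether 6 Hz changes theta or attention remains a matter for the randomised Group x Session comparisons.

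The cost is a change of wording and no new data. The downside is power of about 35 to 37% at 20 per arm for 0.5 versus 0, so the Verum-only statement becomes harder to make even when true. That reflects what this sample size can support and is no reason to omit the term.

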## Dissemination Plan

**Registration.** PI and co-PI will ensure that the clinical trial is registered and results are submitted to ClinicalTrials.gov as outlined in the NIH policy and according to the specific timelines stated in the policy.

**Informed Consent.** Informed consent documents for the clinical trial will include a specific statement relating to posting of clinical trial information at ClinicalTrials.gov. Importantly, it will be clear that privacy will be maintained. Only group averages will be reported in scientific communications. Where individual data are reported (e.g., showing example representations of brain activation), individuals are not identified.

**Compliance.** UCSF internal policy will ensure that clinical trials are registered and results reporting occur in compliance with policy requirements.

## Protection for Human Subjects

### Risks To The Participants.

**a. Human Participants Involvement and Characteristics:** In this proposal, we will recruit people with MS. General inclusion criteria for all participants are: age 18-65, diagnosis of MS (relapsing or progressive) according to McDonald criteria, Expanded Disability Status Scale (EDSS)  $\leq 6.5$ , no paresis of the upper limbs, a minimum of 3 months since the last relapse, no severe depression (Beck Depression Inventory<19), normal hearing, and no changes in MS or symptomatic medications in past 2 months. Exclusion: prior brain surgery, clips in brain, epilepsy or other neurological or non-affective psychiatric disorders, pregnancy. Because of the difficulties in interpreting cognitive studies in participants with English as a second language, only native-English speakers will be asked to participate in the study. Participants will be selected in an unbiased fashion with regard to sex and race. Gender and minority representation issues do not interact with any of our hypotheses. Therefore, the participants that we recruit will be representative of previous populations studied at University of California, San Francisco and will be represented in the approximate proportions that we have listed. Every effort will be made to ensure that the participant population conforms to the NIH policy on Gender and Minority Inclusion in Research Study populations.

**b. Sources of Materials:** Behavioral and EEG data will be collected from each individual. Information obtained from the studies in the research plan will be strictly confidential, except as required by law, but will be made available to the participant in response to a specific request from the participant. All data will be identified only by a code number. There will be only one "key" linking a participant's name and personal information with their code number. This key, and all participant information and data, is maintained in files in locked cabinets in locked lab space or password protected computer files. Only

the Principal Investigator and research staff has access to these files. Typically, only group averages are reported in scientific communications. Where individual data are reported (e.g., showing example representations of brain activation), individuals are not identified.

**c. Potential Risks:**

- **Electroencephalography:** There are no known risks associated with EEG procedures, all of which have been used extensively in previous research. Conventional EEG recording and sensory stimulation techniques with standard subject grounding procedures are always employed. Some electrode paste may remain on the scalp, but it can be easily removed with shampooing.
- **Transcranial alternating current stimulation:** Although uncommon, tACS has some risk for headache, dizziness, nausea, itchy sensation, irritation under the area of the electrodes and the sensation of shock. TACS has also been reported to cause brief flashes of light ("phosphenes") in humans, but these are not discomforting. Should an adverse effect occur in a participant, that participant will be excluded from continuing the intervention. The protocol described here uses stimulation levels that fall well within safety limits established by basic research investigating neural tissue damage and other possible physiological effects in both humans and animals. Overall, tACS is generally considered a safe, noninvasive and painless technique for modulating neural excitability.

**Adequacy Of Protection Against Risks.**

**a. Recruitment and Informed Consent:** Participants will be recruited from the UCSF Center for MS and Neuroinflammation, a clinic that sees over 6,000 patients annually with MS and related disorders. All participants will participate in the informed consent process. They will be familiarized with the protocol by the experimenter, including risks and benefits, and informed consent will be documented according to the regulations governing human beings as experimental participants at the University of California, San Francisco.

**b. Protection Against Risks:** All participants will be under close supervision throughout the experiments. All tACS, and EEG recordings are done with state of the art technology. Equipment is routinely screened to assure all components, cables etc are in perfect working condition and standard grounding techniques are always employed. All information collected from the proposed experiments will remain strictly confidential, except as required by law, and will be made available to the participant and his/her physician upon the participant's request. Personal identification of a subject will be excluded from all scientific communications. TACS studies are closely monitored for subject comfort and tACS will be discontinued if stimulation ever feels painful. Low intensity tACS (2mA peak-to-peak

or less) will be used in the proposed studies, and research utilizing similar stimulation parameters as proposed here have reported no adverse mental or health effects lasting longer than the testing session in normal healthy subjects. Much care will be taken to ensure that stimulation parameters are within the range of published safety guidelines. Although no cases of seizures have been reported using tACS with the proposed stimulation parameters, participants will be screened for past occurrence of seizure and a family history of epilepsy as part of the inclusion/exclusion process. Participants will be fully informed of all procedures and the known and potential risks associated with tACS. Trained personnel will be present during all experimental procedures and all research staff are required to maintain current CPR certification. Drs. [name] (PI), [name] (co-PI), [name] (co-investigator) and [name] (co-investigator) will distinguish between a serious adverse event from a non-serious adverse event and an unanticipated problem. In response to an adverse event, [name], a board-certified neurologist at the UCSF Multiple Sclerosis Center, will monitor participants until they are either deemed fit to go home or are directed to the UCSF Medical Center for additional care. In over 33,000 sessions with over 1,000 participants using stimulation similar to the proposed protocol, there is no evidence for irreversible injury produced by transcranial electrical stimulation (tES) protocols within a wide range of stimulation parameters ( $\leq 40$  min,  $\leq 4$  mA). This includes a wide variety of participants, including persons from potentially vulnerable populations. The analysis consolidates and adds to existing evidence on tES safety and facilitates further research of tES in human subjects (Bikson et al., 2016). A more recent review article suggested that safety is established for low-intensity conventional tES defined as  $<4$  mA, up to 60 min duration per day. Using tACS stimulation, fewer adverse effects were reported compared to tDCS. In specific paradigms with amplitudes of up to 10 mA, frequencies in the kHz range appear to be safe (Antal et al., 2017).

### **Potential Benefits Of The Proposed Research To The Participants And Others.**

Participants may gain some insight into the scientific process and human cognition and, in addition, they may benefit psychologically from knowing that they are participating in important research. Participants may also experience slightly improved cognitive control abilities following tACS. The potential benefits anticipated in improved treatment and management of MS patients with cognitive decline are expected to far outweigh the minimal risks associated with these studies.

